# Statistical Analysis Plan

Analyses will be conducted primarily on the SAS system for Windows Version 9.4 which includes capabilities to test multilevel models that appropriately model both normally and non-normally distributed data as well as missing data. The distributional properties of continuously scaled variables

will be examined for skewness and kurtosis to determine appropriate analytic techniques or normalizing transformations prior to the primary analyses.

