Secondary endpoint/analysis: Using the "current pain" version of the Pain Intensity scale (i.e., "Rate your pain level right now." on a scale from 0-10) we will test acute effects of cannabinoids on pain at the 2-Week Appointment, using three time points: a) Pre administration (before the last edible use), b) Post-1h administration (1 hour after the last edible use), and c) Post 2h administration (2 hours after the last edible use) of the 2-week ad libitum study period. We will test a RCR model in which changes in blood levels of CBD, THC, the CBD x THC interaction time (pre administration, 1-hour post-administration, and 2 hours post administration) and all possible interactions are used to predict pain. All independent variables in this analysis are within-subjects as they occur over time. Thus, we are testing the effect of changes in blood levels of cannabinoids on changes in acute pain. We predict that greater increases in THC and CBD acutely will be associated with greater decreases in pain, and that there will be interactive effects such that those participants with the greatest increases in both THC and CBD will experience the greatest decreases in acute pain.

Other secondary endpoints will be analyzed using the same modeling structure described above as appropriate and include: Pre-administration Pain intensity over the two weeks prior to the 2-Week Appointment (average of current, worst, and average back pain over the prior two weeks); Pre-administration Depression, Anxiety, and Stress subscales of the Depression Anxiety Stress Scale (DASS) over the prior two weeks; the Patient Global Impression of Change scale which asks participants to rate their improvement in pain over the prior two weeks on a 7-point scale (completely gone, much better, somewhat better, a little better, about the same, a little worse, and much worse).

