**Secondary analysis/endpoint:** Using our co-primary measures of cognitive impairment listed above, we will test acute effects of cannabinoids on cognitive impairment at the 2-Week Appointment, using three time points: a) Pre administration (before the last edible use), b) Post-1h administration (1 hour after the last edible use), and c) Post 2h administration (2 hours after the last edible use) of the 2-week ad libitum study period. We will test an OLS regression model in which changes in blood levels of CBD, THC, the CBDxTHC interaction, time (pre-administration, 1hour post administration and 2 hours post administration) and all possible interactions are used to predict acute changes in cognitive impairment. All independent variables in this analysis are within-subjects as they occur over time. Thus we are testing

the effect of changes in blood levels of cannabinoids on changes in acute cognitive impairment. We predict that greater increases in THC and smaller increases in CBD acutely will be associated with greater increases in cognitive impairment, and that there will be interactive effects such that those participants with the greatest increases in THC and the smallest increases in CBD will experience the greatest increases in acute cognitive impairment.

Another secondary endpoint includes the total score from the self-reported subjective cognitive functioning from the Functional Assessment of Cancer Therapy – Cognitive Function (FACT-Cog) scale, which assesses perceived cognitive impairments, abilities, and quality of life.

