# Exploratory Analysis (Specific Aims 1 & 2):

# Daily: Follow-up online message data on marijuana use and pain during 2-week period of ad libitum use

Multilevel modelling via random coefficient regression (PROC MIXED or PROC GLIMMIX in SAS Version 9.4) will be used to test between and within-participant relationships between marijuana use and pain in daily message data. Conditional models will be specified with random and fixed effects of marijuana use (modelled as either yes/no for daily use or as quantity of use) predicting pain intensity or pain interference. To account for repeated measures over time, an autoregressive covariance structure will be used for all models. For the continuous quantity of use measure, following Wang and Maxwell, between- and within-participant effects will be disaggregated by person mean-centering the marijuana quantity variable (subtracting the average quantity of marijuana use for that individual), and including time (in days since baseline) as a covariate to detrend the outcome variable (pain intensity/pain interference) in case there are any linear trends in pain over time. The test of the fixed effect of the person mean-centered marijuana quantity variable indicates whether on average there is a significant within-participant relationship between marijuana quantity of use and pain. The test of the fixed effect of the person-mean marijuana quantity (each individual's own average marijuana quantity) indicates whether there is a between-participant relationship of marijuana quantity of use to pain intensity/interference. Due to the intensive longitudinal nature of the design, we will have more than enough power with n=246 participants to estimate these models. In addition, the random coefficient regression procedures allow us the capability of using modern approaches to the handling of missing data including full information maximum likelihood estimation.

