#### 2-Week Mobile Appointment Procedure and Assessments (Pre, Post 1hr, & Post 2hr time points)

Because we wish to obtain our data while the participant is under the influence of their cannabis product, and because it is not safe to operative a vehicle while under the influence, we will bring our state-of-the-art Mobile Van pharmacology and phlebotomy laboratory to the patient's location to complete all 2-Week Appointment procedures (see Table 3). Prior to taking their last edible of the 2-Week study period, participants will come out to the Mobile laboratory to complete their 2nd blood draw, heart rate, motor and cognitive battery and self-report assessments (including quantity of marijuana use and pain severity over the study period). The blood draw will be a venipuncture of a peripheral arm vein using standard, sterile phlebotomy techniques, and 40 mL of blood will be collected. Participants will then return to their home to take their edible.

After taking their edible product, they will return to the Mobile Laboratory 1 hour later. Because 60 minutes is the average time that CBD and THC levels begin to peak in the blood after oral administration of cannabis extract, assessment of the acute effects of marijuana (e.g., pain, cognition, and inflammation) will begin at exactly 1-hour post-edible consumption (Post 1-hour self-administration).

After peak, cannabinoid levels steadily decrease over the next 2-3 hours and by 4 hours post-ingestion begin to rapidly drop off in blood 44,45 ENREF 82. To account for individual differences in metabolism and sensitivity, patients will be assessed again at 2 hours (Post 2-hr self-administration). Each assessment time point [Baseline & 2-Week (Pre, Post 1-hr & 2-hr) self-administrations] will include a 40 mL venous blood draw, heart rate, questionnaires, and motor & cognitive battery. Thus, including the Baseline Appointment, a total of 160 mL of blood (40 ml x 4 time points) will be collected for the entire study. After completing the Post 2-hour consumption assessments, participants will hand in their ActiGraph device, they will be debriefed, and the RA will escort them back to their home. Participants will then be compensated \$100 in cash for their time and effort during the 2-Week Appointment.

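### The acute cognitive analysis under Hypothesis 3 applies OLS to three repeated scores per participant without allowing for within-person correlation, so its standard errors are invalid

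*Combined protocol and SAP*

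**What the plan says.** The secondary analysis under Hypothesis 3 takes the two co-primary cognitive measures at the 2-Week Appointment: before the last edible, and 1 and 2 hours after it. The model sentence reads "We will test an OLS regression model in which changes in blood levels of CBD, THC, the CBDxTHC interaction, time" and continues "time (pre-administration, 1hour post administration and 2 hours post administration) and all possible interactions are used to predict acute changes in cognitive impairment". The next sentence adds: "All independent variables in this analysis are within-subjects as they occur over time". The prediction, however, is about people: "those participants with the greatest increases in THC and the smallest increases in CBD will experience the greatest increases in acute cognitive impairment".

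The 2-Week Mobile Appointment section confirms the repeated design. Each time point "will include a 40 mL venous blood draw, heart rate, questionnaires, and motor & cognitive battery". The Schedule of Evaluations (Table 4) marks the blood draw, the shopping list test and the NIH Toolbox battery at all three occasions.

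Three other places bear on the point:

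- The acute pain analysis under Hypothesis 1 covers the same three occasions but names another model: "We will test a RCR model in which changes in blood levels of CBD, THC, the CBD x THC interaction time".
- The opening of the Statistical Analysis Plan says that SAS "includes capabilities to test multilevel models that appropriately model both normally and non-normally distributed data as well as missing data".
- The exploratory daily-message analysis has an autoregressive covariance structure and says that "between- and within-participant effects will be disaggregated by person mean-centering the marijuana quantity variable".

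**The concern.** OLS treats every row as independent. A three-level time predictor with all its interactions needs more than one row per participant, and rows from one person are correlated. OLS puts the stable differences between people into the residual variance and uses that variance for every test. Within-person effects are then tested against too much noise. Effects carried by between-person differences can be tested against too little.

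This analysis examines acute cognitive impairment, the harm that the Background section stresses, on both co-primary measures. A test that is too conservative for time and for within-person THC or CBD effects can miss real impairment.

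Two undefined choices decide the size of the error. The first is whether changes are raw levels at three occasions or differences from pre-administration; if differences, the listed pre-administration occasion is zero by definition. The second is how time is coded. The plan also calls the predictors within-subject while predicting a contrast between participants, and does not say which effect tests that prediction.

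**Working it through.** **1. The plan's own power figure.** Power Analysis gives power .88 for N = 246, f² = .04 and two-sided alpha .05. For one coefficient with three predictors the noncentrality is √(f² × N) = √(.04 × 246) = √9.84 = 3.14 on 242 df, and power is .878. The figure reproduces, but it assumes one row per person. The documents give no power for the acute cognitive analysis.

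**2. Does other text supply the missing structure?** No. The SAS sentence describes what the software can do and assigns no model. The autoregressive structure belongs to the daily-message models. The acute pain analysis names random coefficient regression but states neither its random effects nor its covariance.

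**3. Closed form for a purely within-person contrast.** With total variance σ² and intraclass correlation ICC, the true error variance is proportional to σ²(1 − ICC), while OLS uses about σ². The OLS standard error is therefore 1/√(1 − ICC) times the true one. The documents give no ICC; .5 and .8 are assumptions.

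| ICC | SE ratio | Effective critical value (1.96 × ratio) | Actual two-sided error |
|---|---|---|---|
| .5 | 1.41 | 2.77 | .006 |
| .8 | 2.24 | 4.38 | below .0001 |

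**4. Null simulation of the model as written.** The set-up was 246 participants in equal thirds (THC only, CBD only, both), lognormal blood levels, a random-intercept outcome with ICC .5 or .8, the full THC × CBD × time OLS model, and 1,500 to 2,000 replicates per setting. The blood profiles are assumptions: pre-administration at 10% or 50% of the 1-hour level, and the 2-hour level at 90%.

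Time and its interactions had type I error .00 to .04 in every coding, for raw levels and for differences from pre. For THC, CBD and THC × CBD:

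| Time coding | Raw, pre 10% | Raw, pre 50% | Differences from pre (10% profile) |
|---|---|---|---|
| Linear 0/1/2 | .001–.02 | .03–.05 | not run |
| Dummy | .04–.06 | .03–.06 | .04–.06 |
| Centred linear | .04–.08 | .10–.18 | .07–.10 |
| Sum-to-zero | .04–.10 | .10–.16 | not run |

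The same fixed effects with a participant random intercept gave .04 to .06 for every term.

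**5. Separate simulation with a simpler model.** Here time was a main effect only, predictors were normal, the outcome ICC was .3 to .8 and there were 3,000 replicates.

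- Raw levels (predictor ICC .2 to .8): .065–.194 for THC and CBD, .049–.166 for the interaction.
- Person-mean-centred levels: .000–.023 for THC and CBD, .064–.096 for the interaction.
- Two differences from pre per person: .069–.088 for THC and CBD, .054–.067 for the interaction.

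Participant-clustered standard errors brought all of these to about .04–.07.

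**6. Illustrative loss of power.** Suppose a mean shift of 0.15 SD at both post-administration occasions. The noncentrality is 246 × 0.15² × (2/3)/(1 − ICC) = 3.69/(1 − ICC), that is 7.38 at ICC .5 and 18.45 at ICC .8. The 2-df critical value is 5.99. OLS in effect raises it to 5.99/(1 − ICC), that is 11.98 and 29.96. Power is then .28 with OLS against .68 at ICC .5, and .14 against .98 at ICC .8. Simulating the full model (600 replicates, dummy time, predictors centred within occasion) gave .23 against .65, and .14 against .97.

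A within-person THC effect with about .80 power under the random-intercept model had .56 (ICC .5) or .09 (ICC .8) under OLS. That run used person-mean-centred predictors plus person means and no time interactions.

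**The case against.** The strongest defence is another reading of the sentence. The outcome is described as acute change, and the prediction concerns participants with the greatest increases. That could mean one change score per person, where OLS is sound: with 1-hour minus pre scores, type I error was .049 to .057. But time listed with three occasions and all interactions cannot be fitted to one row per person, so this reading does not fit the text. It does show a second valid design, if the plan were rewritten to use one pre-specified contrast.

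Several limits stand:

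- With dummy-coded time, THC, CBD and THC × CBD come out close to nominal; the failure there is in time and its interactions.
- The power figures are illustrative. The THC runs use centring and omit interactions that the plan requires, and the mean-shift runs test a time effect that the plan does not predict.
- The random-intercept comparator matches the model that generated the data, so its good behaviour is expected and does not prove that this covariance is right for the real scores.
- Defining change, time coding and centring are specification points beyond the standard-error defect, and they apply equally to the acute pain model.
- The OLS wording may be a carry-over from the primary paragraphs. The written plan is still what an analyst would follow.

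**Conclusion.** The concern holds. As written, the acute cognitive analysis ignores the correlation among three scores from each participant, and nothing elsewhere in the plan corrects it.

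The firmest result is that time, its interactions and within-person cannabinoid effects are tested too conservatively. For THC, CBD and their product the direction is not fixed, and the same data could be tested at error rates from near 0 to about .18 under choices left open. The sizes rest on assumed ICCs and blood-level profiles; the existence of the error does not, provided that a participant's scores are correlated.

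The reach is limited to a secondary analysis. The primary OLS models for Hypotheses 1 to 3 have one outcome row per person, so they and the sample size are unaffected. It should be fixed, and the fix is easy.

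**What to change.** In the Hypothesis 3 secondary analysis:

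1. Replace OLS with a mixed model (random coefficient regression, as for acute pain) that has a participant random intercept or a stated within-person residual covariance. Write this out under Hypothesis 1 as well, where it is also missing. Use random slopes only if three occasions support them.
2. Define change: either raw levels at three occasions, or differences from pre at the two post-administration occasions.
3. State the coding of time.
4. Enter person-mean-centred THC and CBD together with the person means, following the daily-message analysis. Report within-person and between-person effects separately, and say which one tests the prediction about participants with the greatest increases.

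Step 1 repairs the standard errors; steps 2 to 4 make the analysis reproducible and its target clear. The cost is SAP wording only: no new data, visits or participants. The daily-message section already names the SAS procedures. The change should be made before the dataset is locked.

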# **Power Analysis and Sample Size Requirements**

Sample size was selected to permit analysis of the primary research questions at two-tailed alpha of .05 and power level of .80. Estimates of effect size follow Cohen and were conducted in G\*Power 3. We will rely on cannabinoid blood levels (e.g. THC and CBD and their relevant metabolites) as continuous independent variables to predict study outcomes. Thus, we will be testing regression coefficients in the context of a multivariate model with, in the simplest case, three predictors (THC level, CBD level, and the THCXCBD interaction). With a sample of 246 participants, we will be able to detect effects as small as  $f^2 = .04$  with power = .88. This is critical particularly for hypotheses as in each case we predict interaction effects of THD and CBD in blood. It is well known that tests of interactions in non-experimental, observational designs are notoriously small, and thus it is critical that we are adequately powered to detect small effects.

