# The impact of attrition

It is anticipated that some attrition will occur. Based on our current pilot study and previous marijuana studies, we anticipate a 10-15% attrition rate between the Baseline and the 2-Week Appointment. Though we have not experienced differential attrition by condition, and do not anticipate attrition by edible selection, we assume an approximate 85% retention rate over the course of the primary data collection. To adjust for this attrition rate, we will recruit n≈289 participants.

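### The acute models do not define change in THC and CBD; if it is change from Pre, the Pre level of time carries no exposure, and in the cognitive model its 0 = 0 rows take a 5% test to about 11%

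*Combined protocol and SAP*

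**What the plan says.** For cognition (SAP, Hypothesis 3, secondary analysis) the plan writes: "We will test an OLS regression model in which changes in blood levels of CBD, THC, the CBDxTHC interaction", and continues with "time (pre-administration, 1hour post administration and 2 hours post administration) and all possible interactions are used to predict acute changes in cognitive impairment". The outcome is therefore itself a change, and Pre is listed as one of three time levels.

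For pain (SAP, Hypothesis 1, secondary analysis) it specifies an "RCR model in which changes in blood levels of CBD, THC, the CBD x THC interaction time", with the same three occasions and all interactions. Here the outcome is the current pain rating, not a change in it.

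Both sections say the predictors vary within the participant over time. Both predict that larger acute rises in the cannabinoids go with larger acute changes in the outcome. Neither states the reference point for change, whether time is a factor or linear, or how the Pre observations enter. The section on blood analyses of inflammation separates a long, two-week change, seen at Pre, from short or acute changes at 1 h and 2 h.

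**The concern.** An acute rise produced by one edible at one appointment is naturally measured from the sample taken just before it. On that reading the rise in THC, the rise in CBD and their product are all zero at Pre for everyone, yet Pre is a full level of a time term crossed with those exposures.

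Two things follow. First, a slope on change at Pre cannot be estimated, so what is reported as the effect of change depends on coding. Second, in the cognitive model the Pre outcome is also zero by construction. Those rows contribute no residual but are counted as data, so standard errors come out too small and significance is overstated. These are the plan's specified tests of the acute pain and cognition predictions.

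**Working it through.** **Inputs.** The power section sizes the trial for "analysis of the primary research questions at two-tailed alpha of .05 and power level of .80". It states "With a sample of 246 participants, we will be able to detect effects as small as" f² = .04 at power .88, with "three predictors (THC level, CBD level, and the THCXCBD interaction") in the simplest model. The attrition section says "we assume an approximate 85% retention rate over the course of the primary data collection" and "we will recruit n≈289 participants".

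**The plan's own figures.** One coefficient, df = 1 and 246 − 3 − 1 = 242, noncentrality 0.04 × 246 = 9.84: power 0.878, against the stated .88. Recruitment: 246 / 0.85 = 289.4, against about 289. Both reproduce. They concern the primary models; only N = 246 is carried forward.

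**Rank of the acute design.** The terms are the intercept, ΔTHC, ΔCBD and ΔTHC×ΔCBD, each crossed with time. With time as a three-level factor that is 4 × 3 = 12 columns. Let D1 and D2 mark the 1 h and 2 h rows. If change is from Pre, any exposure term x is zero at Pre, so x = x·D1 + x·D2. This holds for three terms, so rank = 12 − 3 = 9. What remains estimable is three time means plus three slopes at each of 1 h and 2 h: 3 + 6 = 9. Numerical ranks under other readings:

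| Meaning of change | Time as factor: columns / rank | Linear time: columns / rank |
|---|---|---|
| From Pre, three occasions | 12 / 9 | 8 / 8 |
| From Pre, 1 h and 2 h only | 8 / 8 | 8 / 8 |
| From Baseline visit | 12 / 12 | 8 / 8 |
| Successive differences | 12 / 12 | 8 / 8 |
| Person-mean-centred level | 12 / 12 | 8 / 8 |

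**Meaning of the change coefficient.** With time as a factor and 1 h (or 2 h) as reference, it is the slope at that hour. With Pre as reference it has no unique value, and the columns a program drops decide what is printed. With time coded 0, 1, 2, the slope at time t is β + γt. The main effect β is then 2 × (1 h slope) − (2 h slope), an extrapolation to Pre. The average of the two post-dose slopes is β + 1.5γ.

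**Effect of 0 = 0 rows in the cognitive model (time as a factor).**
- With Pre rows: 3 × 246 = 738 rows; residual df 738 − 9 = 729.
- Without: 2 × 246 = 492 rows; residual df 492 − 8 = 484.
- The residual sum of squares is the same, because the Pre rows fit exactly. Spurious df: 729 − 484 = 245.
- Standard-error ratio: √(484/729) = 0.815.
- Rejection rate under a true null: 2 × [1 − Φ(1.96 × 0.815)] = 2 × [1 − Φ(1.597)] ≈ 0.11.

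**Simulation under the null.** 4,000 runs, N = 246, change outcomes with SD 1, correlation 0 or 0.5 between 1 h and 2 h, lognormal exposures (all assumed). Ranges cover the three exposure terms and both correlations.

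| Time | Pre rows | Model SE / empirical SE | Rejection at nominal 5% |
|---|---|---|---|
| Factor | kept | 0.793–0.816 | 10.72–11.22% |
| Factor | dropped | 0.964–1.008 | 4.58–5.62% |
| Linear | kept | 0.812–0.871 | 8.92–10.62% |
| Linear | dropped | 0.959–1.008 | 4.60–5.65% |

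The estimated residual variance is 0.66 with Pre rows and 1.00 without, against a true value of 1.

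**The case against.** The strongest reply is that change from Pre is an inference. The plan never states it. It calls the predictors within-subject, predicts pain rather than change in pain in one of the two models, and elsewhere speaks of a two-week change at Pre. On any of the other three readings in the rank table the design is full rank and the Pre rows carry real exposure data. This stands, and the point is therefore conditional. It does not remove the point: the acute wording favours change from Pre, and two analysts could fit different models from the same text.

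Three stronger conclusions are tempting, and the documents support none of them.
- *That the models cannot test the prediction.* They can: with time as a factor the 1 h and 2 h slopes and their average are estimable under every coding, and with linear time nothing is aliased. What is missing is a named contrast.
- *That random slopes in the pain model are not identifiable with three occasions.* The plan lists no random slopes, and exposures that differ between people can inform such variances across people. Fitting them might be difficult, but that is another matter.
- *That power falls to about 25%.* That figure borrows the effect size and N of the primary power calculation and depends on assumed exposure distributions. It also supposes that the linear-time main effect is the coefficient tested. The plan claims no power for the acute models.

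The 0 = 0 problem does not reach the pain model, where the Pre rating is a real score.

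**Conclusion.** The point holds conditionally. The plan leaves the reference for change and the coding of time undefined in both acute models. If change is from Pre:
- With time as a factor, both designs are rank-deficient by three and the reported change coefficient depends on the reference level. With linear time, that coefficient is an extrapolation to Pre.
- In the cognitive model alone, keeping Pre as an outcome row roughly doubles the type I error, to about 11% with factor time or 9–11% with linear time.

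The 0.815 ratio rests on 246 people with all three occasions, OLS with one residual variance, and equal residual variance at 1 h and 2 h. The linear-time range also depends on the assumed exposures. Both analyses are secondary; the primary models and their .88 power are untouched. The change should be made because the most literal reading of the cognitive model gives invalid tests and the repair is nearly free.

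**What to change.** State in the SAP that change in THC and CBD is from Pre at the 2-Week Appointment, and state how time is coded.
- *Cognitive model:* use only the 1 h and 2 h occasions as outcome rows, with two-level time, the Pre value of the outcome as a covariate, and an allowance for within-person correlation in place of plain OLS.
- *Both models:* name the contrast that tests the prediction, for example the average of the 1 h and 2 h slopes.
- *If time-varying levels were meant:* model levels and outcomes at all three occasions, and say so.

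The cost is wording for two secondary analyses. No data are lost, because the Pre cognitive scores become covariates and the Pre blood levels still define the rises. The plan defers tests of its primary endpoints until the dataset is locked, so the wording can be settled before that.

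### The acute cognition model keeps Pre as a time level in a change-on-change OLS; if change is measured from Pre, single-slope tests run at about 0.11 instead of 0.05

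*Combined protocol and SAP*

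**What the plan says.** The point concerns the Statistical Analysis Plan, Specific Aim 2, Hypothesis 3, Secondary analysis/endpoint. There, "we will test acute effects of cannabinoids on cognitive impairment at the 2-Week Appointment, using three time points": Pre, 1 hour after and 2 hours after the last edible. The Baseline visit is not one of the three. The model is OLS. Its predictors are changes in blood THC and CBD, their interaction, and "time (pre-administration, 1hour post administration and 2 hours post administration) and all possible interactions are used to predict acute changes in cognitive impairment". The plan states the aim of the test as "the effect of changes in blood levels of cannabinoids on changes in acute cognitive impairment".

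The plan does not define the point from which a change is measured, how the Pre row is coded, or whether time is a class factor or linear. It makes no provision for several rows per person.

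The parallel acute pain analysis (Hypothesis 1, Secondary endpoint/analysis) differs in two ways. It is a random coefficient regression, "We will test a RCR model in which changes in blood levels of CBD, THC, the CBD x THC interaction time", and its outcome is pain itself, not its change.

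**The concern.** A change measured from Pre is zero at Pre for everyone, in both outcome and predictors. Those rows hold no information about whether larger cannabinoid rises go with larger cognitive changes. OLS nevertheless counts them as observations, and they fit without error. The residual variance is then averaged over rows of which a third cannot contribute to it, so it comes out too small and every test statistic too large.

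This model is the plan's only specified test of the acute predictions on the co-primary cognitive measures: that THC rises go with impairment and that CBD rises offset it. An unrecognised rise in the false-positive rate could produce a false claim of harm or of protection.

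**Working it through.** **The plan's own figures.** The Power Analysis section sets "two-tailed alpha of .05 and power level of .80" for the primary questions. I take 0.05 as the nominal level here too, since the plan states no other. It goes on: "With a sample of 246 participants, we will be able to detect effects as small as" f² = .04 with power .88, for "three predictors (THC level, CBD level, and the THCXCBD interaction". For one coefficient, the noncentrality is √(0.04 × 246) = √9.84 = 3.137, with 246 − 3 − 1 = 242 df, which gives power 0.878. The figure is reproduced. On attrition, "we assume an approximate 85% retention rate over the course of the primary data collection", and 246/0.85 = 289.4 agrees with about 289 recruited. So 246 is the planned number of completers.

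**Residual degrees of freedom** (change from Pre, time as a class factor, all interactions, complete data):

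- Post-dose rows only: 2 × 246 = 492 rows. Parameters: 2 × (1 intercept + 3 slopes) = 8. Residual df = 484.
- Pre rows kept: 3 × 246 = 738 rows. The design has 3 × 4 = 12 columns, but the three Pre slope columns are all zero, so its rank is 9. Residual df = 738 − 9 = 729.
- The Pre intercept fits the 246 zero rows exactly, so the residual sum of squares is the same in both fits.

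**Effect on the test.**

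- Residual variance is multiplied by 484/729 = 0.664.
- The standard error is multiplied by √0.664 = 0.815, and |t| by 1/0.815 = 1.227.
- Two-sided size of a single within-time slope: 0.110. It is 0.110 to 0.111 for any N from 200 to 289, so moderate loss of data does not alter it.
- Joint F tests are affected more: 0.137 on 2 df and 0.158 on 3 df.

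**Simulation under no effect.** N = 246, 4000 runs per scenario. The correlation between 1-hour and 2-hour residuals is assumed to be 0, 0.5 or 0.7, because the plan gives none. OLS, class time:

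| Test | Pre rows kept | Pre rows removed |
|---|---|---|
| Single 1-hour slope (THC or THC×CBD) | 0.102–0.120 | 0.045–0.055 |
| THC×CBD slope averaged over 1 and 2 hours | 0.105–0.182 | 0.049–0.102 |
| THC×CBD×time | 0.050–0.112 | 0.018–0.052 |

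With linear time the design is full rank (8 of 8 columns) and the zero rows are not fitted exactly. The 1-hour slopes still reject at about 0.10 to 0.11 when the mean change is zero, and at up to 0.31 when it is not.

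**Other readings of change** (stated all-interactions OLS, class time, size of a single 1-hour slope):

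| Reading | Size |
|---|---|
| Raw levels at the three times | 0.048–0.055 |
| Change from the Baseline visit | 0.044 |
| Predictors as change from Pre, outcome as raw score | 0.048 |
| Deviations from own mean, predictors and outcome | 0.059 |
| Deviations from own mean, predictors only | 0.045 |

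**Whether one repair is enough.**

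- Dropping the Pre rows but staying with OLS leaves the averaged slope at 0.06 to 0.10 when the residual correlation is 0.5 to 0.7. With the Pre score as covariate, one run gave 0.078.
- Adding a random intercept but keeping the Pre rows does not work either. In a common-slope version (assumed within-person correlation 0.7, 1000 runs) the THC slope rejected 13.4% with the Pre rows and 6.0% without.

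**The case against.** The strongest reply is that the zeros come from a coding rule that the plan does not state. The same paragraph calls all predictors within-subject variables that occur over time. That would also fit raw levels at three occasions, with change as the interpretation. The parallel pain model predicts a level. The section Blood Analyses of Inflammation speaks of a change at the 2-week Pre draw, which can only be a change from Baseline and need not be zero. On each of these readings the size is close to 0.05.

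This stands to the extent that the inflation depends on the reading. A reader might infer that the false-positive rate doubles whatever was meant, deviations from a person's own mean included. The documents do not support that. With own-mean deviations a rate of about 0.11 appears only if the outcome is also centred and the time interactions are removed, and the plan specifies those interactions.

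The reply does not rescue the text. The paragraph uses change for both predictors and outcome, predicts effects of increases, calls them acute, and lists no occasion before Pre. A change from Baseline would make the Pre row a two-week change, not an acute one. If levels were meant, the paragraph describes a different test from the one it announces. If Pre was to be dropped, time cannot have three levels.

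The reply is also right about estimability. A reader might infer that the THC and CBD effects cannot be estimated. With class time only the slopes at Pre are lost; those at 1 and 2 hours, and their average, remain estimable.

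**Conclusion.** The concern holds, conditionally. Read literally, with Pre as the reference, the stated model tests a single 1-hour or 2-hour slope at about 0.11 instead of 0.05. That figure assumes class time, Pre rows kept, and similar residual variance at the two post-dose times. It does not depend on an assumed within-person correlation. If raw levels were intended, this inflation is absent, but the paragraph must still be rewritten.

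Two wider conclusions might be drawn and should not be. First, the acute pain model is not shown to have an inflated error rate: its outcome is pain itself, so it has no zero outcomes at Pre. It shares only the absence of cannabinoid-change slopes at that time. Second, the primary analyses are untouched: they are separate models with one outcome row per person, predicting the Pre value from blood levels with Baseline adjustment. The point concerns a secondary analysis and should be corrected before the data are analysed.

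**What to change.** In Hypothesis 3, Secondary analysis/endpoint:

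- Define change, for cannabinoids and cognition alike, as the difference from the Pre value at the 2-Week Appointment.
- Keep only the 1-hour and 2-hour rows, so that time has two levels.
- Enter the Pre cognitive score as a covariate.
- Replace OLS with a model that accounts for two rows per person, such as the random coefficient regression already named for acute pain, or an unstructured within-person covariance.
- Test each predicted effect as the slope averaged over 1 and 2 hours.

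The removal of the Pre rows and the change of model are both needed, as the last step of the check shows. If the investigators did mean raw levels, they should say so in place of the change wording and still model the repeated rows: pooled OLS on levels gave 0.049 to 0.098 for a slope averaged over the three times.

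In Hypothesis 1, Secondary endpoint/analysis, it is enough to clarify that cannabinoid-change slopes exist only at 1 and 2 hours.

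The cost is SAP wording and slightly less favourable p-values. No data are lost: in a change-from-Pre model the Pre rows contain only zeros, and the Pre score is retained as a covariate.
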